#### **Secondary outcomes**

Health Orientation

To assess participants' health orientation, the Health Orientation Scale (HOS), a validated scale, will be administered at baseline and follow-ups. The HOS is designed to measure individual differences in health-related attitudes, beliefs, and behaviours. It assesses various psychological and behavioural aspects of how people perceive, manage, and respond to their health. Higher scores on the HOS generally indicate a stronger focus on health-related thoughts, emotions, and behaviours. However, the interpretation depends on the specific dimension being measured. The HOS is a comprehensive measure because it assesses multiple psychological and behavioural dimensions of health, including awareness, anxiety, motivation, control beliefs, social perceptions, and future expectations, providing a holistic understanding of an individual's health-related attitudes and behaviours.

#### Mental health and well-being

Mental health and well-being will be assessed using validated questionnaires designed for similar adult populations. All measures are expected to demonstrate good internal consistency at all time points.

- **Generalized anxiety symptoms** will be measured using the Generalized Anxiety Disorder Assessment-7 (GAD-7), with higher scores indicating greater anxiety symptoms.
- **Depressive symptoms** will be assessed using the Patient Health Questionnaire-9 (PHQ-9), where higher scores will reflect more severe depressive symptoms.

- **Mental well-being** will be evaluated using the Warwick-Edinburgh Mental Wellbeing Scale, with higher scores representing greater positive mental well-being.
- **Self-compassion** will be assessed using the Self-Compassion Scale Short Form (SCS-SF), where higher scores indicate greater self-compassion and reduced self-criticism.
- **Overall well-being** will be measured using the WHO-5 Well-Being Index, with higher scores reflecting better psychological well-being.
- **Quality of life** will be evaluated using the EQ-5D, a standardized instrument assessing five dimensions of health-related quality of life, including mobility, self-care, usual activities, pain/discomfort, and anxiety/depression.
- **Loneliness** will be assessed using the three-item UCLA Loneliness Scale, with higher scores indicating greater loneliness.
- **Social support** will be measured through the Medical Outcomes Study Social Support Survey, where higher scores will denote greater perceived social support.
- **Sleep quality** will be evaluated using the Bernese Sleep Health Questionnaire (BSHQ) for the rapid assessment of sleep health and screening of sleep—wake circadian disorders.

#### Physiological measures

The physiological measures in this study will be collected using a combination of **clinical** assessment, wearable technology and laboratory tests.

#### Clinical assessment

Anthropometric parameters, blood pressure and bioimpedance will be registered during in-person assessments. Additionally, cognitive function will be evaluated using the Mini-Mental State Examination and the Clock Test.

#### Wearable measures

Participants will be asked to wear a **Garmin vívoactive® 5 smartwatch**, which is equipped with advanced sensors to track:

- Heart rate variability (HRV): The smartwatch uses an optical heart rate sensor to measure small variations in the time intervals between consecutive heartbeats. HRV is a key marker of autonomic nervous system function and cardiovascular health.
- **Sleep quality:** The smartwatch tracks sleep duration and stages (light, deep, and REM sleep) using accelerometer data and heart rate variability patterns. It provides insights into sleep efficiency and restfulness.
- Physical activity and stress monitoring: The device continuously records heart rate, oxygen saturation (SpO2), and stress levels, using HRV-based algorithms to assess daily stress exposure and recovery patterns.

Participants will wear the smartwatch for one week at three time points: baseline, first follow-up, and second follow-up. After each monitoring period, they will return the device either in person at the hospital or via a prepaid, self-addressed envelope provided by the research team.

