Physical activity is a reliable lifestyle indicator and can be monitored to evaluate the impact of lifestyle interventions. Heart Rate Variability (HRV) is a general indicator of cardiovascular health. In particular, HRV is a physiological marker of the autonomic nervous system (ANS) function. Improved HRV generally indicates better autonomic flexibility, good relaxation, and better cardiovascular health. It has been proved that improving awareness of HRV after myocardial infarction through biofeedback exercises may favourably impact HRV regulation and, therefore, cardiovascular health. HRV biofeedback may be a valid instrument for raising awareness on CVD risk. Lifestyle significantly impacts sleep quality, which in turn contributes to cardiovascular risk and plays a central role in exacerbating its consequences. Blood pressure

increase, as well as the other pathological lifestyle repercussions, directly contributes to increased cardiovascular risk.

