#### Socio-demographic and condition-related variables

At baseline and after 6 and 12 months, data will be collected on participant demographics, socioeconomic status, and condition-related information, including:

- Demographic variables: Age, gender, marital status, educational level, and occupation status (e.g., volunteering activities). Age and gender will only be asked at baseline.
- Socioeconomic status: Household income level, housing situation, and access to healthcare services.
- Condition-related information: Medical diagnosis, duration of illness, and self-reported symptoms.

 Medication use: A comprehensive list of current medications taken by participants, including dosage and frequency.

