#### 4 STUDY POPULATION AND STUDY PROCEDURES

#### 4.1 Inclusion and exclusion criteria, justification of study population

The study population will consist of male or female patients identified by GPs who meet the following **inclusion criteria**:

- Aged 65 or older
- Resident in the Lugano municipality
- Having access to a GP
- Diagnosed for at least six months with one or more of the following lifestyle-related pathological conditions:
  - o Obesity (BMI ≥30)
  - Obstructive sleep apnea syndrome
  - Type 2 Diabetes Mellitus
  - Chronic Obstructive Pulmonary Disease (COPD) (GOLD 2 or higher)
  - Uncontrolled hypertension
  - Uncontrolled gouty arthritis
  - Metabolic dysfunction and alcohol-related liver disease (MetALD)

To ensure consistency in participant selection, individuals must have a confirmed diagnosis that meets these criteria. No specific treatment regimen or symptom severity threshold is required (except for COPD, since GOLD1 is asymptomatic).

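### Watch-derived HRV is read as autonomic function in all wearers, but that reading fails in atrial fibrillation/flutter or fixed pacing, and the protocol neither excludes nor flags such participants

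*Protocol*

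**What the plan says.** Section 3.2 (Wearable measures) describes the measurement: "The smartwatch uses an optical heart rate sensor to measure small variations in the time intervals between consecutive heartbeats". It then gives the interpretation: "HRV is a key marker of autonomic nervous system function and cardiovascular health". Section 2 supplies the direction: "Improved HRV generally indicates better autonomic flexibility, good relaxation, and better cardiovascular health".

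Two other watch outputs depend on HRV by the protocol's own account. Stress is obtained "using HRV-based algorithms to assess daily stress exposure and recovery patterns", and sleep duration and stages are tracked "using accelerometer data and heart rate variability patterns". The watch is not limited to a subgroup: "Participants will wear the smartwatch for one week at three time points: baseline, first follow-up, and second follow-up".

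Section 4.1 admits anyone "Aged 65 or older" with at least one listed condition, among them obesity, sleep apnoea, type 2 diabetes, COPD and uncontrolled hypertension. The only exclusions concern employment, cognition and mobility. The clinical assessment in section 3.2 and the schedule in Appendix 1 list no ECG or pulse-rhythm check. Arrhythmia and pacemakers are not mentioned in the protocol.

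Section 3.2 (Socio-demographic and condition-related variables) does collect "Medical diagnosis, duration of illness, and self-reported symptoms", plus a medication list, at baseline, 6 and 12 months. Nothing links these data to whether an HRV reading can be interpreted.

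**The concern.** HRV as defined here is a property of the beat intervals. It tells us about the autonomic system only when the autonomic system governs those intervals. An irregular arrhythmia makes the intervals vary for another reason, and fixed pacing holds them nearly constant whatever the autonomic state. A watch that measures the intervals perfectly would still give a number without the meaning the protocol attaches to it.

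There are two separate consequences. For a participant with a stable arrhythmia or fixed pacing, the level is not interpretable and the change over time is mainly noise. For a participant whose rhythm changes between visits, the change itself can point the wrong way: onset of an irregular rhythm raises HRV, which section 2 would read as improvement.

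Section 5.1 compares scores before and after the intervention with paired t-tests, and possibly mixed models or repeated-measures ANOVA. All of these work on means, which one extreme value can move. With only 20 controls, a single participant carries weight.

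**Working it through.** The protocol gives no HRV metric, SD, effect size or prevalence of rhythm disorder, so there is no stated figure to reproduce. From the protocol: 80 experimental and 20 control participants (section 3.3) and a 0.05 significance level (section 5.1), taken here as two-sided. Every other value below is an assumption.

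**1. Direction of the artefact.** I take RMSSD, the root mean square of successive interval differences, as an example metric. For intervals with standard deviation s and lag-one correlation r, RMSSD = s × √(2(1 − r)).
- Sinus-like series (s = 35 ms, r = 0.8): 35 × √0.4 = 22 ms.
- Irregular, uncorrelated intervals (s = 80 to 160 ms, r = 0): 80 × √2 = 113 ms to 160 × √2 = 226 ms.
- Fixed pacing (s = 2 ms, r = 0): 2 × √2 = 3 ms.

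Simulation of 3,000 intervals per series gave 22, 114-225 and 3 ms. Irregular rhythm inflates raw variability and fixed pacing suppresses it. These figures describe raw intervals, not the watch's output.

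**2. Chance that such participants are enrolled.** With assumed prevalence p, the chance of at least one among n is 1 − (1 − p)^n.

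| p | at least one of 100 | at least one of 20 controls | expected in 80 / 20 |
|---|---|---|---|
| 2% | 87% | 33% | 1.6 / 0.4 |
| 5% | 99% | 64% | 4 / 1 |
| 10% | >99.9% | 88% | 8 / 2 |
| 15% | >99.9% | 96% | 12 / 3 |

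This counts people whose level is not interpretable. It is not the rate at which rhythm changes between visits, for which there is no figure.

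**3. Effect of one rhythm switch.** Assume an SD of within-person change of 10 ms (variance 100) and an artefact d of 50 to 150 ms.
- Shift of the arm mean = d/n. Controls: 50/20 = 2.5 ms to 150/20 = 7.5 ms. Experimental arm: 50/80 = 0.6 ms to 150/80 = 1.9 ms.
- Variance of change = 100 + d²/n. Controls: 100 + 2500/20 = 225 to 100 + 22500/20 = 1225, that is 2.25 to 12.25 times the original.
- For scale, the 80 v 20 difference detectable with 80% power is (1.96 + 0.84) × √(1/20 + 1/80) = 0.70 SD, or 7 ms at an SD of 10 ms.

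**4. Can one switch create significance?** Suppose there is no other difference and one control switches.
- Welch, d = 50: 2.5/√(225/20 + 100/80) = 2.5/3.54 = 0.71.
- Welch, d = 150: 7.5/√(1225/20 + 100/80) = 7.5/7.91 = 0.95.
- Pooled, d = 50: variance (19 × 225 + 79 × 100)/98 = 124.2, standard error √(124.2 × 0.0625) = 2.79, t = 0.90.
- Pooled, d = 150: variance (19 × 1225 + 79 × 100)/98 = 318.1, standard error 4.46, t = 1.68 (p about 0.10).

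The outlier inflates the standard error along with the mean, so none of these reaches p < 0.05. The estimate can still move by about a third of the detectable difference (2.5/7) to slightly more than all of it (7.5/7), while the interval widens.

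**The case against.** The strongest reply is that a rule on which wearable records are evaluable belongs in the SAP, which is not at hand and may contain one. Such a rule would need no new procedure. That is fair as to where the full algorithm goes. It does not remove the point: the protocol itself gives HRV an unqualified meaning for a population in which that meaning will not always hold, and a named flag has to be on the case report form before data collection. A general diagnosis field may not capture a pacemaker.

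Section 2 says only that improved HRV generally indicates better function, and section 4.3 promises calibration, matching on pre-existing conditions and adjustment for confounders. The hedge does not say when the reading fails. Calibration cannot correct a wrong interpretation of correctly measured intervals, and adjustment cannot restore meaning to an outcome that has none in that participant.

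Several limits stand. Prevalence, SD and artefact size are all assumed. The protocol does not say whether the watch filters, rejects or blanks irregular beats. Pacing that follows the patient's own atrial rhythm is less affected than fixed pacing.

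A reader might go further than the documents allow in three ways:
- That one affected participant could produce a significant arm difference. The t values above do not support this.
- That stress and sleep also move in the wrong direction. The protocol shows only that they draw on HRV, and sleep tracking also uses the accelerometer.
- That inflated HRV variance would mis-size the later RCT. The protocol does not say that HRV variance will be used for this.

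**Conclusion.** The point holds in a limited form. The autonomic reading in sections 2 and 3.2 is applied to all wearers, and nothing in the protocol identifies those in whom it fails. For them the HRV level is not interpretable, and a change of rhythm between visits can shift HRV against its stated meaning. HRV-based stress may be affected too, and sleep staging to a lesser extent.

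The true size cannot be derived from the protocol. Under the assumed values, one switch among the controls can distort or mask an arm difference but does not by itself produce a significant one. HRV is one of many secondary measures in a feasibility study, and the primary outcome of uptake and feasibility is untouched. The point is worth a wording change before data collection, and is no threat to the study's main aim.

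**What to change.** In sections 3.2 and 5.1:
- Restrict the main analysis of HRV and HRV-based stress to participants without known atrial fibrillation/flutter or a pacemaker at baseline. Apply the same restriction to watch sleep stages as a sensitivity analysis.
- Add a named flag for these conditions to the case report form, filled from the diagnosis and medication data already collected.
- Record new cases at 6 and 12 months and report them by arm. Run the analysis with and without their affected readings, and do not remove them from the main analysis, because that would select on an event after group assignment.
- Keep all participants in every other outcome, and report the number not evaluable for HRV as a feasibility result.

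The cost is protocol wording and one flag. Slightly fewer participants contribute to these measures, some valid sinus-rhythm weeks from people with intermittent arrhythmia are lost, and undiagnosed arrhythmia stays undetected.

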#### Laboratory tests

Blood and urine tests to assess various biochemical markers will be performed.

- Blood tests:
  - o Glycated hemoglobin (HbA1c) an indicator of long-term blood sugar control.

- o **Gamma-glutamyl transferase (GGT)** a marker of liver function, bile duct abnormalities and enzymatic activity induction.
- Uric acid a marker of metabolic health and inflammation.
- o Alanine aminotransferase (ALAT) a marker of liver function.
- Creatinine a marker of kidney health.

#### Urine tests:

- Sodium and potassium electrolytes relevant for cardiovascular prognosis.
- Albumin a marker of kidney health.
- o **Creatinine** to normalize sodium, potassium and albumin excretion.

However, if these tests have already been conducted by the GP within the **previous month**, the basal blood draw and urine tests will not be performed.

#### Consultations and hospitalisations/emergency department accesses

We will administer a short questionnaire to the participant's general practitioner (GP) to collect additional data on the participant following the last follow-up (see the document "Questionario medici"). The questionnaire will include questions regarding the frequency of consultations with the GP in the year prior to the study and since its initiation, as well as the numer of hospitalizations or emergency department accesses before and after intervention. The GP will complete the questionnaire and return it to us by email or using a pre-stamped, self-addressed envelope.

#### Link workers' engagement with participants

To assess the quality of the link workers' engagement with participants, link workers will be asked to document each consultation by taking structured notes after each meeting (see the document "Questionario operatori"). These notes will capture:

- Key discussion points during the session
- Participant preferences and concerns related to cultural activities
- Recommendations made and the rationale for their selection
- Participant engagement levels and expressed motivation
- Barriers or facilitators to participation identified during the interaction

These notes will be systematically analysed to identify salient themes related to feasibility, acceptability, and participant engagement. This qualitative assessment will provide valuable insights into the effectiveness of the link worker's role, informing potential improvements in training, communication strategies, and support mechanisms to optimize the intervention.

#### Socio-demographic and condition-related variables

At baseline and after 6 and 12 months, data will be collected on participant demographics, socioeconomic status, and condition-related information, including:

- Demographic variables: Age, gender, marital status, educational level, and occupation status (e.g., volunteering activities). Age and gender will only be asked at baseline.
- Socioeconomic status: Household income level, housing situation, and access to healthcare services.
- Condition-related information: Medical diagnosis, duration of illness, and self-reported symptoms.

 Medication use: A comprehensive list of current medications taken by participants, including dosage and frequency.

#### 3.3 Study design

The study will follow a mixed-method approach. It will be designed as a **double-arm feasibility study with a control group, incorporating baseline and post-intervention assessments.** A total of 100 participants will be recruited and screened by general practitioners (GPs) collaborating with the Institute of Family Medicine at USI to ensure they meet the inclusion criteria. Of these, 80 participants will be assigned to the experimental group and invited to enrol in an artistic or cultural course, selected from a curated selection based on recommendations from a link worker. The remaining 20 participants, matched to the experimental group in terms of gender, age, and medical condition, will serve as the control group and will not participate in these activities, but will be offered a free ticket for a museum, concert o show. Including a small control group in this feasibility study would allow testing of the randomisation procedure and understanding of how the control group would work. All participants will be monitored over time to evaluate the feasibility of the intervention and to assess its potential short-term and long-term effects, particularly in relation to health orientation and other secondary outcomes.

A qualitative sub-study will be nested within the main study to explore the feasibility, acceptability, and experiences of participants, link workers, and general practitioners. A total of 28 voluntary participants will be interviewed, including family physicians (n=10), link workers (n=3), and study participants (n=15). The qualitative study aims to capture subjective experiences of the artistic and cultural prescription intervention and its perceived impact on health and the patient-physician relationship. Participation will be voluntary, and data collection will continue until thematic saturation is reached. Participants will be contacted by the Institute of Family Medicine and invited to take part to an optional interview. Interviews will be offered at both the first and second follow-up, with second follow-up interviews available only to those who did not participate in the first round. Efforts will be made to include individuals from diverse demographic backgrounds, health conditions, genders, and age groups. Separate semi-structured topic guides will be developed for each stakeholder group (see the document "Griglia intervista" for an overview of the topics that will be addressed with study participants). Physicians will be asked about recruitment processes and their experiences with the intervention, while link workers will provide insights into barriers and facilitators of engagement. Participants will discuss their experiences, including any barriers to participation, whether they found the programme enjoyable and beneficial for their symptoms, and if so, why. Interviews will be audio-recorded with participants' consent. Thematic analysis will be performed on the transcriptions of the interviews following Braun and Clarke's approach.

Successful **participant blinding** in experimental studies strengthens the credibility of the results, because knowledge of the assignment and perception of the treatment may affect outcomes. In this study, participants may perceive that they are receiving superior or inferior care depending on the group they are assigned to, and may consequently report more positive or negative experiences and varying outcomes. This may potentially damage the quality of the data, but also be a source of harm for patients themselves. Hence, we decided to only inform participants of the purpose and procedures of the study in general terms (i.e., evaluation of their outcomes and their experience with an activity), so as to not reveal our specific objectives and the assigned group.

To ensure transparency and respect for participants, there will be a debriefing session after the study's completion. This debriefing will take place through a phone call, where the researcher will provide verbal information explaining the specific objectives and rationale behind the group assignment. Following the call, participants will receive written information at home to ensure they have a clear understanding of the context of their involvement and the results of the study. This written document will serve as a reference to reinforce the spoken explanation and offer an

opportunity for participants to review the details at their convenience (see the document "Debriefing partecipanti").

#### 3.4. Study intervention

A **link worker from the Città di Lugano** will contact participants to provide detailed information about the available cultural offerings and the research procedure. The link worker will work closely with participants to understand their personal preferences and interests, ensuring that the selected cultural activities align with their tastes and needs. By tailoring the experience to each participant, the link worker will help identify the most appropriate events or activities that can enhance their engagement and overall well-being, while also supporting the goals of the research study.

Participants will receive up to six sessions with their link worker, which is a pragmatic allocation based on trial feasibility, though in real-world practice, individuals may receive additional support if needed. Each session will last up to one hour and will be conducted in person, over the phone, or via video call, depending on participant preference and accessibility.

All cultural activities will be **fully funded**, ensuring that financial barriers do not limit participation. The available activities are part of a curated set designed specifically for this program, including drawing, painting, music, photography, museotherapy, dance, and theater. Link workers will not have complete autonomy over referrals but will guide participants toward these pre-selected activities that align with the research framework. Each type of activity will include up to 25 weekly sessions, lasting 1-2 hours each and taking place at LAC. All activities will be facilitated by a cultural facilitator.

We propose participatory artistic activities, as opposed to more passive cultural experiences (such as being a spectator at events). This choice is grounded in the belief that active participation in the creative process fosters deeper emotional engagement, enhances personal expression, and can have therapeutic benefits for mental and physical well-being. By engaging participants in hands-on artistic creation, we aim to encourage a sense of accomplishment and connection to the cultural experience, as well as promote social interaction and personal growth.

Although link workers will not have prior clinical experience, they are trained social workers with expertise in community engagement and participant support. Before beginning their role, they will receive specialized training tailored to the study's objectives, covering aspects such as effective communication, cultural engagement strategies, goal-setting exercises, and data recording procedures.

To enhance participant engagement, link workers will use structured resources, including goal-setting exercises, to help individuals articulate their motivations, expectations, and desired outcomes from the cultural activities. Compliance with attendance at the prescribed cultural events will be closely monitored throughout the study to ensure adherence to the intervention and to assess engagement levels. Furthermore, the communication between the link worker and the GP will be standardized to ensure that the sense and purpose of the prescription are consistently maintained and aligned, avoiding any potential loss of focus regarding the intervention's goals. In this regards, we will adopt best practice such as those suggested in the toolkit on how to implement social prescribing.

Cultural facilitators conducting the activities will also receive specific training on the project. They will be required to possess both expertise in the subject matter of their activities and skills in cultural and social mediation. Their role will include fostering an inclusive and engaging environment while adapting activities to participants' needs. Cultural facilitators will work in close collaboration with link workers, who will, in turn, liaise with general practitioners as needed to ensure a coordinated approach.

